7.2. Deviations, Missing Concentrations and Anomalous Values

In summary tables and plots of median profiles, statistics will be calculated having set concentrations to missing if 1 of the following cases is true:

1. A concentration has been collected as ND (ie not done) or NS (ie no sample);
2. A deviation in sampling time is of sufficient concern or a concentration has been flagged anomalous by the pharmacokineticist.

Note that summary statistics will not be presented at a particular time point if more than 50% of the data are missing.

7.3. Pharmacokinetic Parameters

Actual PK sampling times will be used in the derivation of PK parameters.

If a PK parameter cannot be derived from a subject’s concentration data, the parameter will be coded as NC (ie not calculated). (Note that NC values will not be generated beyond the day that a subject discontinues.)

In summary tables, statistics will be calculated by setting NC values to missing; and statistics will be presented for a particular dose with ≥ 3 evaluable measurements.

If an individual subject has a known biased estimate of a PK parameter (due for example to an unexpected event such as dosing error), this will be footnoted in summary tables and will not be included in the calculation of summary statistics or statistical analyses.

8. STATISTICAL METHODOLOGY AND STATISTICAL ANALYSES

8.1. Statistical Methods

As this is an **CCI** study, no formal hypothesis testing will be performed.

8.2. Statistical Analyses

8.2.1. Pharmacokinetic Analysis

To assess the pharmacokinetics of PF-06755347, the PK parameters detailed in Section 6.3 will be listed and summarized for subjects in the PK analysis set (as defined in [Section 5.2.2](#)). Missing values will be handled as detailed in [Section 7](#). Each PK parameter will be summarized by dose. Optional Cohort 10 Japanese (if applicable) will be analysed separately. Each summary will include the set of summary statistics as specified in [Table 2](#).

Table 2. PK Parameters to be Summarized Descriptively

| Parameter | Summary Statistics |
|--|--|
| AUC _{last} , AUC _{inf} , C _{max} , C _{max} (dn), AUC _{last} (dn), AUC _{inf} (dn), CL, V _{ss} , | N, arithmetic mean, median, cv%, standard deviation, minimum, maximum, geometric mean and geometric cv%. |
| T _{max} | N, median, minimum, maximum. |
| t _{1/2} | N, arithmetic mean, median, cv%, standard deviation, minimum, maximum. |

There will be one summary table split by dose presenting all PK parameters.

To assess the relationship between the PK parameters and dose, dose normalized AUC_{inf} (if data permit), AUC_{last} and C_{max} will be plotted against dose (using a logarithmic scale), and will include individual subject values and the geometric means for each dose separately. Geometric means will have a different symbol than the individual values. The values will be dose normalized (to a 1 mg dose) by dividing the individual values and raw geometric means by dose. A footnote will be added to the plots to indicate that geometric means are presented.

Supporting data from the estimation of t_{1/2} and AUC_{inf} will be listed where applicable: terminal phase rate constant (k_{el}); goodness of fit statistic from the log-linear regression (r²); the percent of AUC_{inf} based on extrapolation (AUC_{extrap}%); and the first, last, and number of time points used in the estimation of k_{el}. These data may be included in the clinical study report.

Presentations for PF-06755347 concentrations will include:

- A listing of all concentrations sorted by subject ID, dose, and nominal time post-dose. The concentration listing will also include the actual times. Deviations from the nominal time will be given in a separate listing.
- A summary of concentrations by dose, cohort, and nominal time post-dose, where the set of statistics will include n, mean, median, standard deviation, coefficient of variation (cv), minimum, maximum and the number of concentrations above the lower limit of quantification.
- Median concentrations time plots (on both linear and semi-log scales) against nominal time post-dose by dose and cohort (all doses on the same plot per scale, based on the summary of concentrations by dose, cohort and time post-dose).
- Mean concentrations time plots (on both linear and semi-log scales) against nominal time post-dose by dose and cohort (all doses on the same plot per scale, based on the summary of concentrations by dose, cohort and time post-dose).

The length of time used for the x-axes of these plots will be decided on review of the data, and will depend on how long PF-06755347 concentration is quantifiable in the matrix.

For summary statistics, median and mean plots by sampling time, the nominal PK sampling time will be used, for individual subject plots by time, the actual PK sampling time will be used.

Subjects having positive ADA may be analyzed separately to assess impact of ADA on PK concentrations and if no effect then those subjects will be included in the summarized PK concentration and parameter descriptive statistics. Refer to [Section 8.3.8](#) for more details.

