2. INTRODUCTION

PF-06755347 is a recombinant human IgG1 multimeric Fc fusion protein which includes the IgG1 hinge region, the CH2, and CH3 domains, with a human IgG2 hinge domain fused onto the C terminus. The molecule is designed to form Fc multimers, in order to enhance avidity to Fc γ receptors (Fc γ Rs).

The current study is the first clinical trial proposed with PF-06755347. It is designed to evaluate the safety, tolerability, pharmacokinetics (PK), as well as potential pharmacodynamic (PD) effect of PF-06755347 following single intravenous (IV) doses of PF-06755347 to healthy adult subjects.

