2.1. Study Design

This is a Phase I, randomized, double-blind (Investigator and subject-blind, sponsor-open), placebo-controlled, parallel, single-ascending dose study of PF-06755347 in healthy subjects, to be conducted at a Pfizer Clinical Research Unit (CRU) that is in very close proximity to a major medical center. Personnel, trained in advanced cardiac life support, emergency resuscitative equipment and the management of anaphylaxis, are immediately available to treat systemic reactions under the supervision of a physician. IV fluids, epinephrine, antihistamine and methylprednisolone will be available for immediate parenteral use in the event of an anaphylactic reaction. In addition, a dedicated ambulance will be present at the research unit during dosing to facilitate rapid transfer to the Emergency Department of a major medical center, if needed.

The study will include 8 planned cohorts, with a provisional ninth cohort optionally added to explore or enhance the understanding of the full dose range. An optional Japanese cohort (Cohort 10) is also included. The optional Cohort 9 and Cohort 10 may or may not be conducted pending evaluation of available safety and PK data from other cohorts and at the discretion of the Sponsor.

[figure not shown]
A total of approximately 73 healthy adult subjects are planned to be randomized. Fewer subjects (N=5, 3 active and 2 placebo) are planned for Cohorts 1-3, which are expected to have plasma exposure below the predicted efficacious concentration range (ie, doses ≤ 1 mg/kg). For Cohorts 4-9 with expected plasma exposure near or exceeding predicted efficacious concentration range (ie, doses > 1 mg/kg), a total of 9 subjects (6 active and 3 placebo) is planned. If pharmacological activity or exposure is significantly greater than expected, the sample size for Cohorts 1-3 may be increased to 9 subjects at the discretion of the Sponsor in consultation with the PI. A total of 4 active subjects are planned for the optional Japanese cohort. A schematic of the overall study design is provided in [Figure 1](#).

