6.3. Pharmacokinetic Endpoints

Blood samples for PK analysis of PF-06755347 will be taken according to the Schedule of Activities given in the protocol.

The following PK parameters will be calculated for PF-06755347 from the concentration-time values using standard non-compartmental methods:

Table 1. Non-compartmental PK Parameters

| Parameter | Analysis Scale | PF-06755347 |
|----------------------------|----------------|-------------|
| C_{\max} | ln | D |
| C_{\max} (dn) | ln | D |
| T_{\max}^* | R | D |
| $t_{1/2}^*$ | R | D |
| AUC_{last} | ln | D |
| AUC_{last}^* (dn) | ln | D |
| AUC_{inf}^* | ln | D |
| AUC_{inf}^* (dn) | ln | D |
| CL^* | ln | D |
| V_{ss}^* | ln | D |

Key: A=analyzed using statistical model, D=displayed with descriptive statistics, ln=natural-log transformed, R=raw (untransformed), *=if data permits

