8.3. Safety Analysis

A set of summary tables split by treatment will be produced to evaluate any potential risk associated with the safety and toleration of administering PF-06755347. The optional Cohort 10 (if applicable) will be presented separately.

No formal analyses are planned for safety data. The safety and other endpoints detailed in [Section 6.2](#) will be listed and summarized in accordance with sponsor reporting standards, where the resulting data presentations will consist of subjects from the safety analysis set (as defined in [Section 5.4](#)).

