8.3.1. Treatment and Disposition of Subjects

Subject evaluation groups will show end of study subject disposition and will show which subjects were analyzed for pharmacokinetics, as well as for safety (adverse events and laboratory data). Frequency counts will be supplied for subject discontinuation(s) by treatment. Japanese subjects in Cohort 10 (if applicable) will be summarized separately from the subjects in other cohorts.

Data will be reported in accordance with the sponsor reporting standards.

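### The SAP still describes the IV-only healthy-subject design, so its by-dose PK-parameter and ADA outputs would pool ITP participants with healthy men, and its Japanese cohort label is out of date

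*SAP*

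**What the plan says.** The SAP lists no amendments (section 1). Its introduction describes dosing "following single intravenous (IV) doses of PF-06755347 to healthy adult subjects", and section 2.1 adds "A total of approximately 73 healthy adult subjects are planned to be randomized" and "An optional Japanese cohort (Cohort 10) is also included". The unredacted text mentions neither SC dosing nor ITP.

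The outputs follow from that design:

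- **PK parameters (SAP 8.2.1).** "Each PK parameter will be summarized by dose. Optional Cohort 10 Japanese (if applicable) will be analysed separately", followed by "There will be one summary table split by dose presenting all PK parameters". The dose-normalised plots show geometric means for each dose.
- **ADA (SAP 8.3.8).** The percentage positive is given by dose, with only Cohort 10 apart. An optional table gives PK parameters by ADA status, with no dose or route split stated.
- **Safety (SAP 8.3 and 8.3.1).** Tables are split by treatment, and "The optional Cohort 10 (if applicable) will be presented separately". For disposition, "Japanese subjects in Cohort 10 (if applicable) will be summarized separately from the subjects in other cohorts".
- **Parameter list (SAP 6.3).** "The following PK parameters will be calculated for PF-06755347 from the concentration-time values using standard non-compartmental methods"; Tables 1 and 2 include CL and Vss but not CL/F, Vz/F or F.

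The current protocol differs. Section 4.1 plans SC Cohorts 7-14. Cohort 10 is a healthy-participant SC cohort, which Table 4 shows in progress. Cohort 12 is the optional Japanese cohort, and Cohorts 13 and 14 are ITP. Section 4.2.1.3.3 allows ITP doses of 25, 50 or 100 mg SC, starting at 25 mg. Table 7 shows all three already observed in healthy participants. Section 2.1 says that no further IV dosing will occur.

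**The concern.** PK and immunogenicity are secondary objectives, and in a study without hypothesis tests the descriptive tables are the analysis. How those tables are grouped therefore matters.

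Healthy participants are men who abstain from other therapies. ITP participants may be of either sex and may continue stable ITP treatment, including corticosteroids, thrombopoietin-receptor agonists or immunosuppressives. Protocol 4.1 says that assessing safety, tolerability and PK in both sexes is important. A row that merges the populations at a shared dose does not report ITP participants separately.

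The safety tables, which serve the primary objective, are split by treatment without saying whether ITP participants form their own group.

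**Working it through.** **1. Which design does the SAP describe?** Cohort sizes from SAP 2.1: Cohorts 1-3 have 5 each, Cohorts 4-9 have 9 each, and the Japanese cohort has 4.

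3 × 5 + 6 × 9 + 4 = 15 + 54 + 4 = 73.

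This reproduces the SAP's total. The SAP is consistent with itself, but for a design of at most 10 cohorts; the protocol now has 14.

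**2. ITP share of a by-dose row.** ITP cohorts have 3 to 6 participants and no placebo (protocol 9.2). Placebo PK specimens are not routinely analysed (protocol 6.3.2), so only healthy actives are counted. Cohort 7 has 3 actives and Cohorts 9-11 have 6 (protocol 4.1). Cohort 8 dosed 8, which at 3:1 is also 6. Protocol 9.2 instead gives the 8-person cohort as 4 active and 2 placebo, which adds to 6 rather than 8. The schematic linking doses to cohorts is not shown, so all three counts are carried.

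Share s = ITP / (ITP + healthy actives):

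| Healthy actives | 3 ITP | 6 ITP |
|---|---|---|
| 3 | 3/6 = 50% | 6/9 = 67% |
| 6 | 3/9 = 33% | 6/12 = 50% |
| 4 (protocol 9.2) | 3/7 = 43% | 6/10 = 60% |

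**3. Possible effect on a geometric mean.** If r is the ITP/healthy exposure ratio, the pooled log mean is the healthy log mean plus s × ln r. Hence pooled / healthy geometric mean = r^s. The documents give no r; 0.5 to 2.0 is assumed.

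| r | s = 1/3 | s = 1/2 | s = 2/3 |
|---|---|---|---|
| 0.5 | 0.79 | 0.71 | 0.63 |
| 2.0 | 1.26 | 1.41 | 1.59 |

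The 43-60% shares lie inside this range. At r = 1 there is no shift.

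**4. Route.** In the PK-parameter table, IV doses are in mg/kg and SC doses in flat mg, so rows stay apart by route. The dose-normalised plots have no route split, and protocol 9.5.1.1 has none either. The optional PK table by ADA status has no dose or route split. As worded, these two outputs mix IV and SC data.

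**5. Japanese label.** Separate-presentation statements naming Cohort 10, by SAP section: 8.2.1 (1), 8.3 (1), 8.3.1 (1), 8.3.5 (1), 8.3.6 (3), 8.3.7 (4), 8.3.8 (3). Total 14. Those in 8.2.1 and 8.3.1 also say Japanese; the other 12 give the number alone.

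**6. Parameters.** Protocol Table 10 assigns CL and Vss to IV, and CL/F, Vz/F and F to SC. SAP Tables 1 and 2 list only the IV pair.

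**7. Is a split feasible?** SAP 7.3 presents statistics when at least 3 measurements are evaluable. ITP cohorts of 3 to 6 can meet this, though a cohort of 3 has no slack.

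**The case against.** The strongest reply is that this is a document out of step with its protocol, in a descriptive study, with time to correct it. Protocol 9.4 says the SAP will be finalised before database lock. Concentration summaries and mean and median plots are by dose and cohort, demographics are by cohort, PK parameters are listed, and the dose-normalised plots show individual values. The study is Sponsor-open and the ITP cohorts are open-label, so regrouping late would not break a blind. CL/F and Vz/F are tertiary endpoints, reported if applicable. All of this stands and limits the harm.

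The protocol wording does not close the gap, however. Sections 9.5.1.1 and 9.7 summarise PK and ADA by treatment group without saying that ITP is a group of its own.

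A reader might infer that the SAP would separate the wrong cohort, presenting healthy Cohort 10 apart and leaving the Japanese participants in the by-dose rows. That requires ignoring the SAP's own definition of Cohort 10 as Japanese in section 2.1, repeated in 8.2.1 and 8.3.1. The intent is recoverable; what is shown is a stale label.

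**Conclusion.** The point holds and should be fixed. Followed as written, the SAP pools ITP and healthy participants at shared SC doses in the PK-parameter table, the dose-normalised plots and the ADA percentages. The ITP share would be 33-67%, assuming planned cohort sizes and evaluable data from all actives; the 4-active count in protocol 9.2 gives 43-60%. The missing route split, the stale label and the absent SC parameters are lesser signs of the same lag.

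It would go too far to say that a pooled row misrepresents both populations. That presumes different exposure, which no document establishes; the 0.63 to 1.59 range illustrates an assumed ratio of 0.5 to 2.0. Nor is there loss of data, or any effect on a hypothesis test (none is planned) or on escalation decisions, which rest on ongoing data review.

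**What to change.** Amend the SAP before database lock:

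- Group PK parameters, dose-normalised plots, ADA (including PK by ADA status) and the safety treatment groups by population (healthy, Japanese, ITP), route and dose.
- Replace every Cohort 10 reference with the Japanese cohort, named by population (now Cohort 12), so that renumbering cannot break it again.
- Report CL and Vss for IV, and CL/F, Vz/F and F for SC, if data permit.

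In the protocol, match the plot wording in 9.5.1.1 and reconcile the active counts in 4.1 and 9.2.

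The cost is one SAP amendment, small protocol wording edits and some table reprogramming. No new data are needed.

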4.2. Statistical Decision Rules

No decision rules are required.

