5.2.2. Parameter Analysis Set

The PK parameter analysis population is defined as all randomized subjects who received at least one dose and have at least 1 of the PK parameters of interest.

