6.6. Other Endpoints

6.6.1. Immunogenicity (ADA)

Response rates of the development of anti-PF-06755347 antibodies (ADA).

Definitions for positive ADA will be determined with the completion of the validation work for the assay and may be included in an amendment to this SAP prior to final database lock.

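### SAP 8.2.1 ties inclusion of ADA-positive subjects in the PK summaries to an undefined finding of no ADA effect, which read naturally selects subjects on their outcome and conflicts with the PK analysis sets

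*SAP*

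**What the plan says.** The last paragraph of SAP 8.2.1 begins with a permission: "Subjects having positive ADA may be analyzed separately to assess impact of ADA on PK concentrations". It continues with a condition: "if no effect then those subjects will be included in the summarized PK concentration and parameter descriptive statistics". The opposite branch is not written.

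Other text that bears on this:

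- SAP 5.2.2: "The PK parameter analysis population is defined as all randomized subjects who received at least one dose and have at least 1" of the parameters of interest. SAP 5.2.1 defines the concentration set in the same way. Neither mentions ADA.
- SAP 8.2.1, opening: PK parameters are listed and summarised, by dose, for the PK analysis set.
- SAP 4.2: "No decision rules are required".
- SAP 6.6.1: "Definitions for positive ADA will be determined with the completion of the validation work for the assay", with a possible SAP amendment to follow.
- SAP 7.3: for parameters that could not be calculated (NC), "statistics will be calculated by setting NC values to missing"; and "statistics will be presented for a particular dose with ≥ 3 evaluable measurements".
- SAP 7.2, for concentrations: "summary statistics will not be presented at a particular time point if more than 50% of the data are missing".
- SAP 8.3.8: spaghetti plots and PK tables by ADA status are possible outputs, optional and subject to the data.
- Protocol Section 3: the PK objective concerns the study population. Protocol 9.7 says only that the effect of positive ADA on PK will be assessed where appropriate.

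**The concern.** A condition for inclusion has a purpose only if failing it leads to something else, and the natural alternative is to leave the subject out. Subjects would then be dropped because their PK differed. Whenever the condition acts, the main summary stops describing everyone who was dosed and describes the subjects whose PK ADA did not alter. Reported exposure would be too high if ADA speeds clearance and too low if ADA prolongs exposure.

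Nothing in the SAP says how the effect is to be judged, by whom or when, and positive ADA itself is not yet defined. Two analysts could produce different main tables from the same data.

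PK is a secondary endpoint. If ADA incidence differed between doses and the geometric means in the dose-normalised plots followed the same rule, apparent dose proportionality could be distorted. In the smallest dose groups, one omission can also remove the parameter summary.

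**Working it through.** **1. Group sizes.** SAP 2.1 plans Cohorts 1-3 with 3 active and 2 placebo, Cohorts 4-9 with 6 active and 3 placebo, and an optional Japanese cohort of 4 actives. The total is 3×5 + 6×9 + 4 = 15 + 54 + 4 = 73, which reproduces the SAP's figure of approximately 73. Groups of 3 actives remain in the current protocol: Cohort 7 has 3 active and 1 placebo (Section 4.1), and the ITP cohorts have 3 to 6, all active (Table 4). Protocol 9.2 reports no formal sample size calculation, so there is none to check.

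**2. The texts side by side.** SAP 5.2 and the opening of 8.2.1 put every dosed subject with data into the summary. The end of 8.2.1 makes that conditional for ADA-positive subjects. If the condition fails, only one of the two can be followed.

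**3. Shift in the geometric mean.** Let k of n actives be left out, with exposure r times that of the others, whose geometric mean is G. Over all n the geometric mean is G·r^(k/n); after omission it is G. Reported over true is r^(−k/n). The documents give no value for r, so a range is assumed:

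| Left out | r = 0.8 | r = 0.5 | r = 0.3 |
|---|---|---|---|
| 1 of 6 | 1.038 (+4%) | 1.122 (+12%) | 1.222 (+22%) |
| 2 of 6 | 1.077 (+8%) | 1.260 (+26%) | 1.494 (+49%) |

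With r above 1 the shift is downward.

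**4. Suppression with 3 actives.** This assumes that a subject left out does not count as evaluable, and that the omitted concentrations count as missing.

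- Parameters: 3 − 1 = 2, below the minimum of 3 in SAP 7.3, so no summary is shown. That rule is per dose, so a repeated or expanded dose level could still reach 3.
- Concentrations: 1/3 = 33% missing, within the 50% limit of SAP 7.2, so the summary stays. With two left out, 2/3 = 67%, and it goes.

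**5. Chance of having enough ADA-positive subjects.** The documents give no human rate. Protocol 2.2.2 reports 11% in rats and 62% in monkeys, used here only as an assumed range p.

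- At least 1 of 3: 1 − (1 − p)³. At 11%, 1 − 0.89³ = 0.295. At 62%, 1 − 0.38³ = 0.945.
- With 6 actives, at least 4 must be left out before fewer than 3 remain. The binomial probability of 4 or more ADA-positive among 6 is 0.002 at 11% and 0.586 at 62%.

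These are upper limits for losing a parameter summary, because an ADA effect must also be judged present and the subject then left out.

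**The case against.** The strongest reply is that the SAP never orders an exclusion. The separate analysis is optional, the other branch is unwritten, and the main instruction is to summarise the PK analysis set. A reader might infer a stated exclusion rule, and the documents do not go that far. It stands that this is a reading of the text. But a condition with no consequence would be pointless, and leaving the consequence unstated is itself a defect.

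The condition may also never act. The paragraph of protocol 2.2.2 that gives the 62% monkey rate adds that exposures were generally similar in ADA-positive and ADA-negative monkeys. It concerns weekly dosing for up to 6 weeks, whereas this trial gives one dose. This stands, and it limits the expected size.

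Little would be hidden. Concentrations and parameters are listed for each subject, and the dose-normalised plots show individual values. This stands too. The by-status tables help less: they are optional, and if the minimum of 3 applies to them, a 2/1 split of 3 actives leaves both strata without statistics.

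One might add that an ADA effect cannot be judged at all with 3 to 6 actives. The SAP does not confine the judgement to one cohort, and dose-normalised parameters could be pooled across doses. The firmer point is that no criterion is given.

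Finally, the SAP describes an older IV-only design. The conflict is nevertheless in its current text, and groups of 3 actives persist in the protocol.

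**Conclusion.** The point holds as a conflict within the SAP and with the PK objective. Read naturally, the conditional sentence selects subjects on their outcome, with no criterion and an unwritten second branch. It should be corrected, although all the PK analyses are descriptive and the condition may never be met.

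Three stronger conclusions are tempting and are not supported:

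- **That exposure will be overstated by a known amount.** Taking 30% ADA-positive at half the exposure gives 1/0.5^0.30 = 1.23, a 23% overstatement, but both inputs are invented. The documents fix neither size nor direction. The 4%, 12% and 22% for 1 of 6 rest on the assumed ratios.
- **That a 3-active dose group has a 30% to 95% chance of losing its summary.** That is the chance of at least one ADA-positive subject at assumed rates of 11% to 62%, and only an upper limit for the loss. The loss concerns the parameter summary; the concentration summary survives one omission and individual listings remain. Nor can bias and suppression from one omission both affect the parameter summary of a group with only 3 actives: if the summary is suppressed, no biased mean is reported.
- **That dose escalation is compromised.** The PK limits in protocol 6.7 apply to exposure in any individual participant, not to these summary means.

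**What to change.** Delete the conditional inclusion sentence from SAP 8.2.1. State that the main PK concentration and parameter summaries include all subjects in the PK analysis sets of SAP 5.2, whatever their ADA status. Keep the PK tables and spaghetti plots by ADA status in SAP 8.3.8 as supplementary output.

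A 3-active dose group then keeps its 3 subjects, and its parameter summary cannot be lost because of ADA.

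The cost is one SAP sentence. The by-status outputs are already foreseen, and the amendment that SAP 6.6.1 anticipates for the definition of positive ADA could carry the change before database lock.
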